### Training Session: Baseline Tasks and MRI Scans (Visit 1)

During the Training Session, subjects will be familiarized with the experimental tasks and procedures of the experimental sessions. Subjects will be familiarized with TMS during the training session using a single-pulse TMS procedure that will be used to determine resting motor threshold (RMT) during experimental sessions. Briefly, the volunteer will be seated in a chair and the MagVenture C-B60 TMS coil will be positioned against the subject's scalp over the primary motor cortex. Single magnetic pulses from the TMS coil will be used to locate the region of the primary motor cortex that controls the hand and fingers, with the goal of limiting TMS-pulse-induced motor responses to the thumb and first finger. Single TMS pulses will then be administered and the stimulation output intensity will be adjusted using either the adaptive PEST algorithm for non-parametrically estimating TMS motor thresholds (<http://www.clinicalresearcher.org/software.htm>) and/or the Rossini-Rothwell method using electromyographic (EMG) recording equipment. The Rossini-Rothwell method determines the minimum single-pulse intensity necessary to produce motor evoked potentials (MEPs) of at least 50 microvolts (uV) peak-to-peak amplitude in at least 50% of pursued trials (e.g., 5 or more of 10 trials).

Subjects will also be escorted to the Magnetic Resonance Imaging and Spectroscopy Center (MRISC) at the UK Medical Center to perform the battery of cognitive assessments (described under Data Collection) while in the MRI scanner during the training session. Neuroimaging data will be acquired using a Siemens 3-Tesla (3T) PRISMA scanner as described under Data Collection below. Subjects will not undergo MRI scanning during the 6 experimental sessions.

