determined by its current value and delta, the reward prediction error, defined in Equation 2 as the difference between the obtained or omitted reinforcer minus the outcome expectation that is determined by the reinforcement history for that option. The learning rate parameter (alpha) then determines the magnitude of expected value updating for option A. Finally, the probability of choosing A is determined via a softmax decision rule according to Equation 3, where the probability of choosing option A is a function of the difference between the values for A and B, multiplied by beta, a “temperature” parameter that alters the likelihood of the differential values between the alternatives dictating the predicted choice. Finally, A and B choices from the previous trial ( $C[a](t-1)$  and  $C[b](t-1)$ ) are multiplied by a perseveration parameter (“c”, the propensity of the individual to make the same choice on the current trial, regardless of reinforcement history). The free parameters alpha, beta, and c will be estimated using maximum likelihood estimation and differences (delta) in model fits estimated using Akaike’s Information Criterion (AIC) and pseudo r-squared, with parameters compared by model comparison and linear mixed modeling (Burnham & Anderson, 2002; Gelman & Hill 2006; McFadden 1974). Importantly, the RL modeling framework is flexible, and further decision-making complexities (e.g., outcome-specific learning rates or differential future-reward discounting) can be included when warranted. The alpha level will be set at the  $p<0.05$  for all analyses.

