**Neuroimaging Data Analyses:** Brain activity and functional connectivity patterns will be associated with PRLC task outcomes and cannabis use demographics. For traditional analyses, separate first-level fixed-effects general linear models (GLMs) will be performed for each subject using SPM12 (Friston et al., 2007; Wesley et al., 2016). For molar analyses, blood-oxygen-level dependent (BOLD) signals associated with each condition of interest (selection and feedback event times for each choice alternative and control trials) will be convolved with the hemodynamic response function (HRF) and contrasted (choice events > control) to produce activity maps of each choice of interest. For molecular analyses, trial-by-trial RL modeling parameters (learning rate  $\alpha$  and reward prediction error  $\delta$ , and the perseveration parameter “ $c$ ”) will be parametrically regressed against the observed BOLD signal for events of interest (choice and feedback times for each choice option). Similarly, connectivity analyses will be performed using the psychophysiological interaction (PPI) method for both molar and molecular analyses (see Figure 2). In this case, first-level GLMs will contain interaction terms generated from primary eigenvariate timecourses extracted from corticostratial ROIs and the aforementioned conditional and parametric event times of interest. All first-level outputs will be moved forward to second-level random effects GLM analyses examining activity and connectivity between groups and correlating demographic variables with brain maps. Analyses will be performed with the hypothesis-driven corticostratial ROIs and a whole-brain mask for exploratory analyses. Voxel-wise statistical thresholds will be set to  $p<0.001$  with contiguous voxel extent thresholds set to 5 and 20 for ROI and whole-brain analyses, respectively. Small volume family-wise error correction for multiple comparisons will be applied.

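### Learning rate alpha and perseveration c are fitted constants in the plan's own choice model, so as trial-by-trial fMRI modulators they add nothing to the event regressors

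*Combined protocol and SAP*

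**What the plan says.** Two parts of Data Collection & Research Materials bear on this, together with the Visit 1 section.

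- **Behavioral Data Analyses** sets out the reinforcement-learning model: "The free parameters alpha, beta, and c will be estimated using maximum likelihood estimation". Alpha scales each value update. The text glosses c as "the propensity of the individual to make the same choice on the current trial, regardless of reinforcement history". Model fits are compared by AIC and pseudo r-squared, "with parameters compared by model comparison and linear mixed modeling". Delta is defined as obtained outcome minus current expectation, so it changes from trial to trial. Extensions are left open: "further decision-making complexities (e.g., outcome-specific learning rates or differential future-reward discounting) can be included when warranted".
- **Neuroimaging Data Analyses** specifies one first-level GLM per participant. Its molecular sentence starts "For molecular analyses, trial-by-trial RL modeling parameters (learning rate", adds delta and c to the list, and says that these "will be parametrically regressed against the observed BOLD signal for events of interest (choice and feedback times for each choice option"). The PPI models then use "the aforementioned conditional and parametric event times of interest". The second-level sentence names group comparisons and correlations with demographic variables.
- **Training Session: Baseline Tasks and MRI Scans (Visit 1)** states: "Subjects will not undergo MRI scanning during the 6 experimental sessions". Each participant therefore has one scanned session.

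**The concern.** The behavioural text treats alpha and c as estimates that summarise a person's choices. The imaging text treats them as quantities that change from trial to trial. Only delta, the option values and the previous-choice terms change by trial in the model as described.

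Followed literally, the alpha and c columns are redundant with the event columns or empty, so there is no alpha or c map to carry to the second level. A misleading map, in which the ordinary event response is labelled as alpha or c, would arise only if the modulator were left uncentred and the event term omitted.

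The question these parameters can answer is a between-person one: do participants who learn faster, or perseverate more, differ in brain response? The imaging section opens by promising to relate brain patterns to PRLC task outcomes, but its second-level sentence does not name the fitted parameters.

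**Working it through.** The plan gives no figure to reproduce. The check concerns the rank of the first-level design.

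**Inputs from the documents.** Alpha, beta and c fitted by maximum likelihood; delta defined per trial; choice and feedback events for each of two options; one scanned session; TR 2 s; 480 trials and 45 minutes as the task's example limits (45 × 60 / 480 ≈ 5.6 s per trial).

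**Step 1: algebra.** With response function h and event times t_i, the event regressor is x(t) = Σ h(t − t_i), and a modulator with weights w_i is m(t) = Σ w_i h(t − t_i).
- If w_i = k on every trial, m(t) = k·x(t), which is exactly collinear with x.
- If the weights are mean-centred, w_i − k = 0 and m(t) = 0.

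This holds for any k, event timing or response shape.

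**Step 2: numerical check.** One simulated scan of 480 trials at TR 2 s. Assumed: alpha 0.35, beta 3, c 0.4, event timing and a double-gamma response. The base design has 4 event regressors (choice and feedback × two options) plus an intercept, 5 columns in all. Each modulator adds one column per option.

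| Added to the base design | Columns | Rank | Share of modulator not explained by events |
|---|---|---|---|
| nothing | 5 | 5 | n/a |
| alpha | 7 | 5 | below 1e-27 raw; zero column if centred |
| c | 7 | 5 | below 1e-27 raw; zero column if centred |
| delta | 7 | 7 | 98% |
| c × previous choice | 7 | 7 | 65% raw, 76% centred |

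**Step 3: other layouts.** 40 simulated scans (20 participants × 480 or 120 trials; alpha 0.1-0.8, beta 1-5, absolute c 0.1-1), raw and centred, gave the same pattern. The rank deficit always equals the number of alpha and c columns.
- All three modulators at all 4 events: 4 + 3 × 4 = 16 columns. Alpha and c supply 8 of them; rank 16 − 8 = 8.
- c at choice, alpha and delta at feedback: 4 + 3 × 2 = 10 columns. Alpha and c supply 4; rank 6 (7 of 11 with an intercept).

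**Step 4: outcome-specific learning rates.** In the 10-column layout the rank rises to 8: the two alpha columns become estimable and the two c columns do not. Trial alpha then takes one value after reward and another after no reward. In absolute value it correlates 1.000 with reward versus no reward, and 0.79-0.98 (median 0.90) with delta.

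**Step 5: PPI.** With seed s(t) and task term p(t), a constant modulator gives s(t)·k·p(t) = k·[s(t)·p(t)], a multiple of the unmodulated PPI term. With the event PPI in the model, adding the alpha or c PPI gave rank 3 of 4; the delta PPI design had rank 5 of 5.

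**Step 6: does the replacement work?** Value difference and repeat/switch at choice, with delta at feedback, give 4 + 3 × 2 = 10 columns. Rank was 10 in all 40 scans, with maximum variance inflation 1.5, 2.0 and 1.3 respectively.

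**Step 7: why the previous-choice indicator should not be scaled by c.** The same simulated response, refitted with previous choice multiplied by c, gave these coefficients:
- c = 0.1: 10.37
- c = 1: 1.04
- c = −0.5: −2.07

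Absolute t was 37.1 each time. Coefficient × c is about 1.04 throughout (10.37 × 0.1; 1.04 × 1; −2.07 × −0.5). Scaling by c would therefore make participants' coefficients differ by a factor 1/c, including its sign, with no difference in brain response.

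**The case against.** The algebra is not in dispute. The stronger objections are about what the authors meant and how much it matters.

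- **c may be shorthand.** In the model, c appears only as a multiplier of the previous choice, and that product does vary by trial and is estimable (rank 7 of 7). This is a plausible intention. The imaging text nevertheless names the parameter itself, so it would still need correcting, and Step 7 shows why the scaled product is a poor regressor. Alpha has no comparable reading in the base model.
- **The equations are in an attachment that was not available.** They could show a trial index on alpha or c, so this caveat applies to the activity models as well as to PPI. PPI is less certain still, because Figure 2 was also unavailable. Against that, the prose describes all three equations and gives neither parameter an update rule.
- **The model may be extended.** True, but outcome-specific rates only make alpha recode reward, and c remains constant.
- **The harm is limited and would show itself.** Largely right. The usual result is a missing map, not a false one, and the primary outcomes are behavioural. But the Data Monitoring Plan starts participant-level analysis as data arrive, so a substitute chosen when the model fails would be chosen with data in hand.
- **The replacement modulators are partly a matter of preference.** This stands for the choice between value difference and choice probability. It does not touch the need to replace alpha and c at the first level.

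**Conclusion.** The concern holds. In the base model as described, two of the three named molecular modulators, and the PPI terms built from them, cannot be estimated separately from the event terms. The loss is complete for those terms: each alpha or c column adds nothing to the rank.

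This rests on one inference, that alpha and c are fitted once per participant and session. The maximum-likelihood wording, the description of c as an individual's propensity and the absence of any trial-wise update all support it. The rank result does not depend on the simulated parameter values or timing; the variance inflation and the correlation with delta do.

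Delta maps, molar maps and the behavioural primary outcomes are untouched. This is a correction the plan should make to a secondary imaging analysis and does not threaten the trial's main conclusions.

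**What to change.** In Neuroimaging Data Analyses:

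1. Restrict first-level parametric modulators to quantities that vary by trial. At feedback, use delta. At choice, use the expected-value difference or the model's choice probability, plus a repeat-versus-switch indicator not multiplied by the fitted c.
2. Enter each participant's fitted alpha and c (and beta if wanted) as between-participant covariates in the second-level GLM, and name them in that sentence.
3. Build the molecular PPI terms from the same trial-varying quantities.
4. State that if outcome-specific learning rates are adopted, alpha will not be used as a modulator, because it would only recode reward.

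The cost is analysis wording. The training-session scan and the fitted parameters are already planned, so no new data or procedures are needed.

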#### Attachments

Attach Type	File Name
DataCollection	N-Back Instructions and Worksheet.pdf
DataCollection	PRLC Envelope Instructions.pdf
DataCollection	Cannabis Purchase Task Instructions.pdf
DataCollection	Specific Items on the VAS.pdf

#### Resources

Describe the availability of the resources and adequacy of the facilities that you will use to perform the research. Such resources may include:

- Staffing and personnel, in terms of availability, number, expertise, and experience;
- Computer or other technological resources, mobile or otherwise, required or created during the conduct of the research;
- Psychological, social, or medical services, including equipment needed to protect subjects, medical monitoring, ancillary care, or counseling or social support services that may be required because of research participation;
- Resources for communication with subjects, such as language translation/interpretation services.

This study will take place at the NSL and MRISC, which contain all the necessary physiologic, computer, brain stimulation, and imaging equipment for the study. [name] is an adult psychiatrist who has worked extensively with individuals with substance use disorders in both the clinical and research setting and he is the responsible medical investigator for this study. He will be available to attend to medical problems as well as any psychological or psychiatric issues that may arise. [name] (PI), [name] (Co-I), and their investigator-level colleagues will provide scientific oversight for the study and have safely completed numerous human behavioral pharmacology studies. Overall, the study team and resources described above are well equipped to protect participants and successfully implement, carry out and complete this study protocol.

#### Potential Risks & Benefits

##### Risks

- Describe any potential risks – including physical, psychological, social, legal, ability to re-identify subjects, or other risks. Assess the seriousness and likelihood of each risk.
- Which risks may affect a subject’s willingness to participate in the study?
- Describe likely adverse effects of drugs, biologics, devices or procedures participants may encounter while in the study.
- *Qualitative research* - describe ethical issues that could arise while conducting research in the field and strategies you may use to handle those situations.
- Describe any steps to mitigate these risks.

##### Benefits

- Describe potential direct benefits to study participants – including diagnostic or therapeutic, physical, psychological or emotional, learning benefits. This cannot include incentives or payments.
- State if there are no direct benefits.
- Describe potential benefits to society and/or general knowledge to be gained.

Describe why potential benefits are reasonable in relation to potential risks. If applicable, justify why risks to vulnerable subjects are reasonable to potential benefits.

The behavioral, subjective and physiological assessment procedures employed in these experiments are benign. Adverse events identified as possible risks in this study include:

1. The risk that the subject's protected health information (PHI) may be viewed by others not directly involved in the conduct of the proposed research.

2. Possible embarrassment in disclosing sensitive personal information.

3. Possible discomfort due to study procedures.

4. Possible dissatisfaction with the study procedures.

5. Side effects associated with the physiological and behavioral effects of the study drug.

With respect to side effects, the dose of THC to be administered in the proposed research has been administered safely to human subjects under controlled laboratory and medical conditions. The relative safety, as well as the contraindications and possible side effects of THC are well known and documented. However, the administration of any drug involves some risks simply because individuals differ in their reactions to drugs.

Common side effects of cannabinoid agonists such as cannabis and THC include anxiety, asthenia, ataxia, myalgia, akathisia, tachycardia, palpitations, arrhythmias, hypotension, flushing, abdominal pain, nausea, vomiting, diarrhea, constipation, dry mouth, headache, change in appetite, cognitive and mood disturbances (e.g., euphoria, paranoia, depersonalization, amnesia, confusion and memory impairment), sleep disturbances and nightmares, speech difficulty, dizziness, sedation, somnolence, hypothermia and shortness of breath. It is likely that subjects will experience one or more of these side effects. In addition, these drugs may exacerbate psychiatric symptoms in individuals with certain mental health disorders (i.e., mania, depression or schizophrenia). Unsupervised self-administration of higher doses of cannabis has resulted in more serious side effects such as psychotic episodes and panic attacks. It is unlikely that subjects will experience these more serious side effects. In addition, seizures can occur in subjects with existing seizure disorders. The occurrence of seizures appears to be related to the presence of certain predisposing factors including histories of head trauma, CNS tumors and previous incidence of seizures. Individuals reporting any of these predisposing factors will be excluded from participation, so the risk of seizure is extremely low. In addition, cannabis interacts with other licit and illicit drugs and alcohol. All subjects will be monitored for use of unauthorized drugs throughout the study and will be appropriately cautioned about their activities before and after their participation, so the risk of interactions with other drugs is also low.

6. Side effects associated with brain stimulation.

There are no known health risks associated with TMS at the output intensities and duration of stimulation proposed in this application (Huang et al., 2005; Chung et al., 2016; Lowe et al., 2018). It is not uncommon, however, for some subjects to experience skin sensations under the stimulation coil (e.g., itching, tingling, twitching). These sensations typically occur immediately after stimulation begins and subside shortly thereafter as the skin desensitizes. Participants will be made aware of this possibility prior to stimulation and asked to report any such sensations if they occur. If sensations occur that are irritating to subjects, stimulation will be paused and adjustments will be made to the stimulation equipment to help alleviate irritation (e.g., repositioning the coil, scratching the skin to alleviate an itch). Another side effect that has been reported with TMS is a tension-type headache, which can be treated with over-the-counter (OTC) pain relievers and tend to resolve naturally over time (Rossi et al., 2009). Subjects will be informed of this possibility and asked to report any headaches that occur following TMS during experimental sessions. Subjects who report headache following TMS will be advised on what OTC pain relievers (and what doses) are approved for use by the study physician without special permission. The study physician will be consulted in the event that a subject reports severe and/or persistent headaches and a determination will be made regarding their continued participation in the study. Although not expected, we will ask subjects to report any burning sensations that may be indicative of physical burns. If a subject reports a burning sensation under a TMS coil, then stimulation will be stopped immediately and the skin will be examined for redness and soreness. If a subject's skin appears to be abnormally irritated and/or if a subject continues to report a burning sensation, then the protocol will be halted and they will be withdrawn.

The current study uses MagVenture stimulation devices, coils, and stimulation protocols that are cleared by the FDA and/or are within the safety limits for the use of TMS in humans. TMS delivery has been associated with an increased risk of seizure, we therefore exclude individuals who report a history of seizures and/or epilepsy. Although the occurrence of TMS-induced seizures is rare and unexpected given the stimulation parameters and procedures used, should a participant experience a TMS-induced seizure, the TMS protocol will immediately be stopped and the participant will be monitored until the event resolves (Rossi et al., 2009b). Additionally, the participant will be moved to the floor and oxygen will be administered via a bag valve mask once the seizure passes. The study physician will be contacted and available should further medical intervention be necessary. If the seizure is deemed serious enough by the study physician, an ambulance will be called to provide medical assistance to the participant if they agree to it. It is also possible that participants could experience syncope (i.e., fainting) during the TMS session. Should a participant experience a syncopal event, the TMS protocol will immediately be stopped, the participant will be moved to the floor, and monitored until they regain consciousness. Syncopal events are more common than seizures in the context of TMS but tend to resolve naturally very quickly (Rossi et al., 2009b). In the event of any SAEs (seizures or syncopal events), the NSL staff recommend the participant does not drive themselves home. An emergency contact number provided at screening will be contacted to pick the participant up. The safety profile

of TBS protocols is comparable to that of other repetitive TMS protocols (Oberman et al., 2011). Of note, in a clinical setting, patients receive an FDA-approved TMS protocol (e.g., iTBS or 10 Hz repetitive TMS) once daily for 4 to 5 days a week for 5 to 6 weeks. In addition, the FDA-approved 10 Hz repetitive TMS protocol that is used clinically delivers a total of 3000 pulses across a 19-minute period whereas the TBS protocols used in this study will deliver a total of 900 pulses during one, approximately 4-minute and 40-second (iTBS) or 60-second (cTBS) bout of stimulation during each session. Our research study will test a single bout of TMS per session, approximately 3 hours after capsule administration, across three real and three sham stimulation sessions of equivalent duration (each separated by at least 48 hours) in cannabis users.

